iASSIST and 73.9% conventional outliers of $\pm 2^\circ$ from neutral for the tibia slope⁹. The improvement of the accuracy achieved by the use of the iASSIST Knee validation feature will be evaluated as part of the study for both femur and tibia cuts in both planes. The first tibial proximal and the first femoral distal cuts will be performed and validated. If the validation values are outside of ± 2 degrees from target, the surgeon will adjust the cut as per the iASSIST surgical technique recommendations, re-cut and re-validate.

Table 1. Predefined Target Component Angles

Plane	Component	Persona component Angles
Frontal	Femoral	90
	Tibial	90
Sagittal	Femoral	defined by preoperatively
	Tibial	defined by preoperatively

SAMPLE SIZE

This sample size calculation was conducted anticipating the use of a Fisher’s exact test.

Alpha level: 5% (two-sided)

Power: 80%

Assuming we anticipate that 95% of the investigational group has an angle deviation within $\pm 2^\circ$ and that for the control group, 70% have an angle deviation within $\pm 2^\circ$, the calculation for sample size when comparing proportions is 31 patients. 50 patients per group comfortably exceeds 20% attrition. Therefore, this provides for a total of 100 patients for both arms.

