7.3 DATA ANALYSES

Data will be analyzed using SAS 9.0 or higher. The Type I error rate for the primary study analysis will be 0.05. Comparisons for secondary, exploratory, and safety analyses will be two-sided comparisons using $\alpha = 0.05$, with no adjustment for multiple comparisons.

Primary Analysis: The primary analysis will be presented as both intention-to-treat (ITT) and Full Analysis set (FAS). In the ITT analysis for the primary endpoint, missing data will be treated as described in Section 7.2. A two-tailed Fisher’s Exact Chi-Square test at $\alpha = 0.05$ will be used to assess the study hypotheses and determine whether there is a statistically significant difference between investigational and control groups with regard to the proportion of patients with femoral or tibial component alignment within +/- 3 degrees from predefined angles (Table 1).

Secondary Analysis: Analyses for secondary endpoints will be FAS, and will only use those cases with complete data for the endpoint being analysed.

Continuous data (e.g. age, BMI, VAS pain) will be reported using mean, standard deviation, median, and range. Comparisons of Investigational vs Control with regard to continuous baseline and secondary outcomes will be performed using standard statistical tests and will be chosen as appropriate for the scale and distribution of the measures being analyzed. For example, a t-test, Wilcoxon test, or one-way ANOVA (as appropriate) may be performed to assess differences.

Categorical data (e.g. gender) will be reported using frequency and percentage. Comparisons of Investigational vs Control with regard to categorical baseline, secondary and safety outcomes will be performed using standard statistical tests and will be chosen as appropriate for the scale and distribution of the measures being analyzed. For example, categorical outcomes may be compared for investigational and

control groups using the Fisher's Exact test (for 2x2 tables) or the Likelihood Ratio chi-square test (for tables larger than 2x2).

Knee prosthesis survivorship will be assessed using a Kaplan-Meier analysis. Comparison of survivorship for Investigational vs Control will be done using the Log-Rank test.

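### The stated 31 patients gives about 66% power, not 80%, with the plan's own Fisher's exact test; 39 evaluable per group are needed, so 20% attrition is covered only narrowly

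*Combined protocol and SAP*

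**What the plan says.** Section 7, under Sample Size, gives the full set of inputs. On the test it says "This sample size calculation was conducted anticipating the use of a Fisher’s exact test". Alpha is 5% two-sided and power is 80%. On the rates, "we anticipate that 95% of the investigational group has an angle deviation within" ±2°, and "for the control group, 70% have an angle deviation within" ±2°. The result is that "the calculation for sample size when comparing proportions is 31 patients". The text does not say whether this is per group or in total; the next sentence, "50 patients per group comfortably exceeds 20% attrition", makes sense only if 31 is per group.

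Section 7.3 confirms the test for the primary analysis: "A two-tailed Fisher’s Exact Chi-Square test at" α = 0.05. Section 2 gives 1:1 allocation.

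**The concern.** The sample size should be calculated for the test that will be used. Fisher's exact test is conservative in small samples, so it needs more patients than an uncorrected large-sample formula. The figure of 31 is lower than the usual uncorrected formulas give for these rates, which suggests that it was not calculated for Fisher's test.

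The attrition statement depends on that figure. The number of evaluable patients is a real constraint here, because the endpoint needs a CT scan at 6 months. Section 7.2 drops from the primary analysis patients lost to follow-up without a 6-month tibial alignment, and Section 3.3 replaces only patients who have no surgery or are found intraoperatively to be ineligible for the implant. If 31 to 38 patients per group were evaluable, the plan would imply that its power target had been met when it had not.

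**Working it through.** **Inputs** (Section 7, Sample Size, unless noted): p₁ = 0.95, p₂ = 0.70, difference 0.25; two-sided α = 0.05; target power 0.80; 1:1 allocation (Section 2); two-sided Fisher's exact test (also Section 7.3); 50 enrolled per group.

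**Step 1: try to reproduce 31.** With z₀.₉₇₅ + z₀.₈₀ = 1.960 + 0.842 = 2.802, whose square is 7.849, the usual formulas give per group:

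- Unpooled normal: (0.95×0.05 + 0.70×0.30) × 7.849 / 0.25² = 0.2575 × 7.849 / 0.0625 = 32.3, so 33.
- Pooled normal, with mean rate 0.825: [1.960√(2×0.825×0.175) + 0.842√0.2575]² / 0.0625 = 35.06, so 36.
- Pooled with continuity correction: (35.06/4) × [1 + √(1 + 4/(35.06×0.25))]² = 42.7, so 43.
- Arcsine: h = 2·arcsin√0.95 − 2·arcsin√0.70 = 0.708; 2 × 7.849 / h² = 31.3, so 32 if rounded up.
- One-sided exact Fisher: 34 (power at 31 is 76.5%).

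The nearest to 31 is the uncorrected arcsine approximation. That it is the source of 31 is an inference, and the finding does not depend on it.

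**Step 2: exact power of the stated test.** Power(n) = Σᵢ Σⱼ Bin(i; n, 0.95) × Bin(j; n, 0.70) × 1[two-sided Fisher p(i, j) ≤ 0.05], summed over all tables with n per group.

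| Evaluable per group | Exact two-sided Fisher power |
|---|---|
| 31 | 65.6% |
| 36 | 75.9% |
| 38 | 79.2% |
| 39 | 80.7% |
| 40 | 82.1% |
| 50 | 89.9% |

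The smallest n that reaches 80% is 39. Exact power does not rise at every step (84.6% at 42, 84.4% at 43), but it stays above 80% at every n checked from 39 to 51.

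**Step 3: attrition.**

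- If 31 were enough: 1 − 31/50 = 38% tolerable loss. The plan does not state this figure; it is implied by 31 out of 50.
- With 39: 1 − 39/50 = 22%.
- Enrolment needed to keep 39 after 20% loss: 39/0.8 = 48.75, so 49 of the 50 planned.
- After 20% loss, 40 per group remain. The spare is 40 − 39 = 1 patient per group, not 40 − 31 = 9.

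**Step 4: sensitivity to the rates.** Section 7 cites outlier rates of 4.8% and 30.4% for the varus-valgus angles. Using 95.2% and 69.6% instead of the rounded rates, power at 31 is 68.2% and 38 per group are needed. Rounding therefore does not explain 31.

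**The case against.** The strongest reply is that the trial enrols 50 per group, not 31. At 50 the power target is exceeded, and at the plan's own 20% attrition 40 per group still give 82.1%. The claim that 50 per group covers 20% loss therefore remains true. Nothing in the plan uses 31 as an enrolment target or a minimum evaluable number, and the 66% would apply only after a loss of 38% in each group, which the plan does not anticipate. All of this stands, and it limits the consequence: the total, the test and alpha need not change. It does not make 31 correct for the named test, and it does not support the word comfortably when the slack is one patient per group.

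A second reply is that correcting 31 to 39 could give false assurance, because the 95% and 70% are rates within ±2°, whereas the primary analysis in Section 7.3 uses ±3° (Section 7 itself uses both). This also stands. Neither 31 nor 39 establishes power for a ±3° endpoint. That conflict is a separate matter, but any corrected power statement has to name the ±2° threshold and the two rates.

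**Conclusion.** The concern holds. Under the plan's own inputs, 31 per group gives 65.6% power, 14.4 percentage points below target, and the requirement is 39 per group, 8 more than stated. The attrition that 50 per group can absorb is 22%, against an implied 38%.

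This rests on reading 31 as per group (if it were a total, the shortfall would be larger), on equal loss in the two groups, and on 95% versus 70% within ±2°. It is an error in a key design figure that cannot be reproduced with the named test. It does not call for more patients under these assumptions.

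**What to change.** In Section 7, Sample Size, replace the figure of 31 with 39 evaluable patients per group, and say that it comes from exact power of the two-sided Fisher test. Replace the attrition sentence with text along these lines:

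> Assuming 95% versus 70% within ±2° and a two-sided Fisher's exact test at 5%, 50 patients per group give about 90% power with no attrition and 82% with 20% attrition (40 per group). Power falls below 80% if fewer than 39 per group are evaluable.

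The calculation should be repeated if the ±2° versus ±3° question is settled in favour of a threshold with different expected rates.

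The cost is wording only. The total of 100 is unchanged, and the plan reports a less favourable margin for missing CT scans.

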7.1 DETAILED DESCRIPTION OF RANDOMIZATION

In this study, patients will be randomized in one of the two treatment arms: *Persona* TKA with *iASSIST Knee* system (Investigational group) or *Persona* TKA with conventional instrumentation (Control group). The randomization scheme is based on equal numbers per group. The randomization will occur via a random number generator (computer) using blocked randomization procedure. The PI or his/her team does not have influence on the randomization scheme. Sealed opaque envelopes, which will be prepared based on predetermined randomization assignment, will be provided to each study site before study initiation.

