2. STUDY DESIGN

The study is a prospective, non-blinded, randomized multi-center study, comparing the use of *iASSIST Knee* versus conventional instrumentation in the hands of experienced surgeons. A total of 100 subjects will be recruited prospectively and randomized according to a 1:1 scheme.

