2.2 NUMBER OF SITES AND SUBJECTS

A total of 100 subjects will be enrolled and randomly assigned to either the investigational or the control group. This study will be conducted at a maximum 6 Japanese sites.

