13.4 SUBJECT CONFIDENTIALITY

The CRFs do not include any patient identifying information. Therefore, once the data is entered in the online database a patient can no longer be identified.

By assigning patients a unique ID number, their identity is protected in the online database. The database is restricted, allowing a doctor to only view and enter data from his/her own patients. User authentication is required to view the data. The data is transmitted to a centralized database through a secured (SSL) channel on the Internet. Data in transit is in 128-bit encryption. The access to the centralized database is limited to those who are responsible for maintaining the database.

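### Section 7.1 sends blocked assignments to the sites in envelopes before the start, with no stated rule on numbering, custody, opening or reconciliation, in a non-blinded trial

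*Combined protocol and SAP*

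**What the plan says.** Section 7.1 describes how the list is made: "The randomization will occur via a random number generator (computer) using blocked randomization procedure". It then describes how the list reaches the sites: "Sealed opaque envelopes, which will be prepared based on predetermined randomization assignment, will be provided to each study site before study initiation". The one further safeguard in that section is: "The PI or his/her team does not have influence on the randomization scheme".

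Section 2 sets the context: "The study is a prospective, non-blinded, randomized multi-center study". Section 2.2 adds: "This study will be conducted at a maximum 6 Japanese sites". Section 2.5 places assignment after consent, and section 13.3 requires a consent log with subject ID and signing date. Section 11 has the sponsor track enrolment and monitor data at least once a year.

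The documents do not state the block size, whether it varies, whether each site has its own list, whether envelopes are numbered, who holds them, when one may be opened, what is recorded at opening, or whether used and unused envelopes are counted. No central or web allocation is described.

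**The concern.** Concealment means that whoever decides to enter a patient cannot know the next arm. Here the whole set of assignments is at the site from the start, and staff see every past assignment because the trial is open. That leaves two routes to foreknowledge. One is to open an envelope early or out of order. The other is to count within a block.

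Foreknowledge matters only if it can change who is entered. Section 3.2 admits femorotibial angles from 175 to 190 degrees, so knees of differing deformity are eligible, and site staff choose whom to approach and when. In-range alignment (the primary endpoint) and operating-room time (a secondary endpoint) could plausibly depend on how difficult the knee is. If easier knees went to one arm, the comparison would shift with no device effect. The independent CT reading does not help, because the distortion would arise at entry and not at measurement.

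**Working it through.** The plan gives no figure on this point to reproduce. The check has two parts: what the text prevents, and how large the effect could be.

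**1. The text.** The statement that the PI's team has no influence on the scheme covers generation of the list, not custody or opening of the envelopes. Sealing and opacity stop someone reading through the paper. They do not stop early opening, and without numbering, a log or a count nothing would reveal it. The consent log identifies patients, but is not tied to envelopes.

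**2. Predictability within a block.** Assumption: fixed 1:1 blocks of size 2k, run within site, with the size known to the site.
- Share of assignments known with certainty = 1/(k+1). Blocks of 2, 4, 6, 8 and 10 give 50%, 33%, 25%, 20% and 17%.
- Best guess (name the arm that is behind), block of 4: the four positions are guessed correctly with probability 1/2, 2/3, 2/3 and 1. The mean is 2.833/4 = 71%. Enumeration for 2, 6, 8 and 10 gives 75%, 68%, 67% and 65%. Full concealment gives 50%.

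**3. Size of the false difference.** Let h be the hit rate, and let easy and hard knees succeed with probability pE and pH, the same in both arms. If an easy knee is entered whenever iASSIST is expected and a hard one otherwise, the expected false difference is (pE − pH)(2h − 1). For complete blocks of 4, 2h − 1 = 0.417:
- 90%/60%: 0.30 × 0.417 = 12.5 points
- 80%/60%: 0.20 × 0.417 = 8.3 points
- 80%/70%: 0.10 × 0.417 = 4.2 points

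If every assignment is seen ahead, h = 1 and the differences are 30, 20 and 10 points.

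**4. False-positive rate.** Simulation with no device effect, 100 patients, six sites of about 17 (equal recruitment is assumed), two-sided Fisher test at 0.05, and every site steering whenever it has a best guess. Unfinished last blocks bring the 12.5 points down to about 12.

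| Assumed easy/hard success | No steering | Blocks of 4 | Blocks of 6 | Sizes 4/6/8 mixed | All seen ahead |
|---|---|---|---|---|---|
| 90%/60% | 3–4% | about 22% | about 16% | about 16–17% | about 94% |
| 80%/60% | about 3% | about 10% | about 8–9% | about 8% | about 54% |
| 80%/70% | 3–4% | about 5% (4–6% across runs) | about 5% | about 5% | about 17% |

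Exact enumeration of the last column with exactly 50 per arm gives 93%, 52% and 16%.

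**5. Weaker steering.** At 80%/60%, steering only on certain assignments gives 7.5% with blocks of 4 and 4.3% with blocks of 10. Seeing a quarter of assignments ahead gives 5.7%. At 90%/60% with blocks of 4, if each site has a one-in-three chance of steering, the rate is 6.1%.

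**The case against.** The strongest reply is that the envelopes are sealed and opaque, that patients consent before assignment, and that looking ahead would be misconduct and not a feature of the design. Omitting the block size from a protocol that sites hold may be deliberate and is good practice. The larger figures need every site to steer every predictable entry, with a suitable knee always available.

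Much of this stands, and it rules out several stronger readings that a reader might infer:
- **That sites will know upcoming assignments, or that the comparison is biased.** Looking ahead requires breaking a seal. Block deduction requires a guessable size and within-site lists, neither of which is stated.
- **That the sponsor's database can already release allocations.** Section 13.4 says "The database is restricted, allowing a doctor to only view and enter data from his/her own patients", which describes data entry and access. It mentions no allocation function, and section 8.2 also allows paper forms.
- **That central release or varied blocks would end guessing.** Past assignments stay visible in an open trial. Mixed sizes 4/6/8 leave about the same false-positive rate as fixed blocks of 6.
- **That no analysis could help.** The femorotibial angle has to be assessed for eligibility, and section 7.3 plans baseline comparisons. Imbalance in that measure could be seen and adjusted for if it is recorded. Selection on unmeasured difficulty could not.

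The objection does not answer the main point: the plan states nothing that would prevent or reveal an envelope opened early or out of order, and that route needs no knowledge of block size.

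**Conclusion.** The point holds as an avoidable weakness in allocation concealment. It is not an error in the plan and not evidence of bias.

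The look-ahead route follows directly from what section 7.1 states and omits. The block-counting route is conditional on a small, guessable block size and within-site lists. The size of either depends on easy and hard success rates and on steering behaviour that the documents do not give. Under best-guess steering in blocks of 4, the false-positive rate runs from about 5% to about 22% over the assumed rates. With all assignments seen ahead it runs from about 17% to about 94%. With large blocks, or with steering by only some sites, inflation is small or absent. The change is worth making because it is cheap and closes the route with the largest possible effect.

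**What to change.** In section 7.1:
- **Main change.** Release one allocation at a time from a central or web system, only after consent, confirmed eligibility and the patient ID have been recorded and locked. Confirm first whether the sponsor's database can do this.
- **Fallback, only where a site cannot use such a system.** Keep envelopes that are sequentially numbered and tamper-evident. Write the patient ID and date on the outside before opening, and reconcile all used and unused envelopes at monitoring.
- **Secondary.** Vary the block sizes and do not disclose them to sites. This removes certainty about block ends but reduces guessing only slightly.

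The cost is modest set-up work and some loss of offline convenience at sites. No patients, visits or changes to treatment are added.

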7.2 HANDLING OF MISSING AND INCOMPLETE DATA

Data will be considered “missing” for the primary endpoint if this outcome cannot be determined or is unavailable for a subject. Every effort will be made to collect the data necessary to evaluate the primary endpoint. Patients who have been lost to follow-up and do not have Tibial alignment at 6 months will not be included in the primary study analysis.

Sensitivity analyses will be performed to assess the impact of missing data on the primary study analysis. These analyses may include a best-case and worst-case imputation as well as a tipping point analysis.

7.3 DATA ANALYSES

Data will be analyzed using SAS 9.0 or higher. The Type I error rate for the primary study analysis will be 0.05. Comparisons for secondary, exploratory, and safety analyses will be two-sided comparisons using $\alpha = 0.05$, with no adjustment for multiple comparisons.

Primary Analysis: The primary analysis will be presented as both intention-to-treat (ITT) and Full Analysis set (FAS). In the ITT analysis for the primary endpoint, missing data will be treated as described in Section 7.2. A two-tailed Fisher’s Exact Chi-Square test at $\alpha = 0.05$ will be used to assess the study hypotheses and determine whether there is a statistically significant difference between investigational and control groups with regard to the proportion of patients with femoral or tibial component alignment within +/- 3 degrees from predefined angles (Table 1).

Secondary Analysis: Analyses for secondary endpoints will be FAS, and will only use those cases with complete data for the endpoint being analysed.

Continuous data (e.g. age, BMI, VAS pain) will be reported using mean, standard deviation, median, and range. Comparisons of Investigational vs Control with regard to continuous baseline and secondary outcomes will be performed using standard statistical tests and will be chosen as appropriate for the scale and distribution of the measures being analyzed. For example, a t-test, Wilcoxon test, or one-way ANOVA (as appropriate) may be performed to assess differences.

Categorical data (e.g. gender) will be reported using frequency and percentage. Comparisons of Investigational vs Control with regard to categorical baseline, secondary and safety outcomes will be performed using standard statistical tests and will be chosen as appropriate for the scale and distribution of the measures being analyzed. For example, categorical outcomes may be compared for investigational and

control groups using the Fisher's Exact test (for 2x2 tables) or the Likelihood Ratio chi-square test (for tables larger than 2x2).

Knee prosthesis survivorship will be assessed using a Kaplan-Meier analysis. Comparison of survivorship for Investigational vs Control will be done using the Log-Rank test.

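### The primary Fisher exact test runs at about half its nominal 5% level because it is discrete; a prespecified site-stratified CMH or Boschloo test would recover about 3 to 9 points of power with no extra patients

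*Combined protocol and SAP*

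**What the plan says.** Section 7.3 makes a two-tailed Fisher exact test the primary test and says that it "will be used to assess the study hypotheses and determine whether there is a statistically significant difference between investigational and control groups". It adds that "The Type I error rate for the primary study analysis will be 0.05". There is no site term, and no analysis in section 7 mentions site. No effect estimate or confidence interval is named for the primary endpoint.

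The sample-size text in section 7 also anticipates Fisher's test, at 80% power and two-sided 5%. It reads "Assuming we anticipate that 95% of the investigational group has an angle deviation within" ±2°, against a control group in which "70% have an angle deviation within" the same limit. It arrives at 31 patients, and 50 per group are enrolled to cover 20% attrition.

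On allocation, section 7.1 says: "The randomization will occur via a random number generator (computer) using blocked randomization procedure". Sealed envelopes "will be provided to each study site before study initiation". Section 2.2 says: "This study will be conducted at a maximum 6 Japanese sites". Neither section says whether blocks are formed within site, and no block size is given.

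**The concern.** In small samples Fisher's test cannot use its full nominal level, because only a limited set of p-values is attainable. The waste is worst when failures are few, as they would be here if alignment is good. With 50 patients per arm at most, and 40 after the planned attrition, several points of power are lost for no gain in protection beyond the stated 5%.

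The plan also hands blocked envelopes to each of up to six sites, and site stands for surgeon and CT scanner. If allocation is restricted within site, the usual practice is to analyse within site too. What is at stake is efficiency, together with a site-adjusted effect estimate that the plan now lacks. The validity of the test is not in question.

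**Working it through.** **Inputs.** From the plan: 95% versus 70% within ±2°, two-sided 5%, 80% power, 50 per group with 20% attrition (50 × 0.80 = 40), and at most six sites. Assumed, because the plan gives no value: a normal site effect on the logit scale with SD 0 to 1.5, six near-equal sites, and 1:1 allocation within each site.

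**Step 1: the plan's own figure.** Fisher's power is the sum over all (x, y) of Bin(x; n, 0.95) × Bin(y; n, 0.70) × 1{p_Fisher(x, y) ≤ 0.05}. Exact enumeration gives:

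| n per group | Fisher power |
|---|---|
| 31 | 65.6% |
| 38 | 79.2% |
| 39 | 80.7% |
| 40 | 82.1% |
| 50 | 89.9% |

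Reading 31 as per group, it does not reproduce for Fisher's test, which needs 39. It is close to a large-sample arcsine formula: 2(1.960 + 0.842)² / (2 asin√0.95 − 2 asin√0.70)² = 31.3. After 20% attrition, 40 per group is one patient above the 39 needed.

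**Step 2: Fisher's true size.** This is the same sum with a common rate p in both arms:

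| Common rate | 40 per arm | 50 per arm |
|---|---|---|
| 70% | 2.8% | 3.1% |
| 82.5% (midpoint of 95% and 70%) | 2.7% | 2.6% |
| 90% | 1.7% | 1.8% |
| 95% | 0.4% | 0.7% |
| Maximum over all rates | 3.3% | 3.5% |

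There is no site effect in this calculation. The cause is visible by hand. At 40 per arm, if all k out-of-range knees fall in one arm, p = 2 × C(40, k)/C(80, k):
- k = 4: 2 × 91,390/1,581,580 = 0.116
- k = 5: 2 × 658,008/24,040,016 = 0.055
- k = 6: 2 × 3,838,380/300,500,200 = 0.026

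With five or fewer out-of-range knees in total, Fisher's test cannot reject, however they are split. At a common rate of 95%, the expected total is 80 × 0.05 = 4.

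**Step 3: alternatives, with and without site.** The CMH statistic without continuity correction is [Σ(x₁ᵢ − tᵢ/2)]² / Σ tᵢ(2nᵢ − tᵢ)/(4(2nᵢ − 1)). Here nᵢ is the number per arm at site i and tᵢ the total in range at that site. Each cell below is power at 95% versus 70%, then size at a common 82.5%. There were 20,000 simulations per setting, with the average rates held at the plan's values.

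| Per arm, site SD | Fisher | Pooled chi-square | Stratified CMH | Exact stratified CMH |
|---|---|---|---|---|
| 40, 0 | 81.9 / 2.79 | 88.7 / 5.24 | 88.3 / 5.05 | 80.7 / 2.53 |
| 40, 0.5 | 82.0 / 2.47 | 89.2 / 4.96 | 89.1 / 4.95 | 81.6 / 2.38 |
| 40, 1.0 | 80.2 / 1.82 | 88.7 / 4.32 | 89.3 / 4.95 | 82.2 / 2.27 |
| 50, 0 | 89.6 / 2.59 | 94.7 / 5.44 | 94.1 / 5.05 | 89.8 / 2.63 |
| 50, 0.5 | 89.4 / 2.48 | 94.6 / 5.21 | 94.4 / 5.14 | 90.2 / 2.71 |
| 50, 1.0 | 87.9 / 1.70 | 93.6 / 4.14 | 94.3 / 4.95 | 90.1 / 2.49 |

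At SD 1.5, Fisher falls to about 79% at 40 per arm and 87% at 50, while CMH reaches about 91% and 95%. At 40 per arm, over common rates of 70-95% and including very unequal sites (14, 10, 7, 5, 3 and 1 per arm), CMH size was about 2.8-5.2%. The low values came at the highest rates.

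**Step 4: separating the two sources of gain.** Pooled chi-square minus Fisher isolates discreteness: 88.7 − 81.9 = 6.8 points at 40 per arm with no site effect. CMH minus pooled chi-square isolates site: 88.3 − 88.7 = −0.4 at SD 0 and 89.3 − 88.7 = +0.6 at SD 1.0, rising to about 2 points at SD 1.5. If 95% and 70% are instead the rates at a typical site, so that the average rates move closer together as sites spread, the site gain at SD 1.5 is 86.7 − 81.7 = 5.0 points.

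**Step 5: an exact option without site.** Boschloo's test keeps its maximum size at or below 5%. Its power is 85.6% at 40 per arm and 92.5% at 50, which is 3.5 and 2.6 points above Fisher. The uncorrected pooled chi-square is more powerful (88.8% and 94.8% by enumeration), but its size reaches 5.9% and 5.7%.

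**The case against.** The strongest case for leaving the plan alone is that nothing in it is invalid. Fisher's test controls type I error and is named consistently in the sample-size text and in section 7.3. On the plan's rates it has 82.1% power at 40 per arm against a target of 80%. Preferring an exact test when failures are few is a legitimate choice. All of this stands, and it limits the point to efficiency.

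Three stronger readings are tempting, and the documents do not support them.
- A reader might infer that ignoring site causes the halved level. It does not: Fisher's size is already 2.6-2.8% with no site effect, and an exact test stratified by site has much the same level (2.3-2.7%). A site SD of 1.0 lowers Fisher's size by about one further point.
- A reader might infer that the analysis contradicts a site-stratified randomization. Section 7.1 does not describe one. A single blocked list divided among sites fits its wording equally well. Nor do the documents give any site, surgeon or scanner variance.
- A reader might use the ±3° cut-off in section 7.3 to argue for stratification. If deviations were normal and centred on target, 95% and 70% within ±2° would become about 99.7% and 88% within ±3°. At 40 per arm with no site effect, Fisher would then have 31.8% power, pooled chi-square 67.4% and CMH 66.5%. That gap owes nothing to site, and the rates are not in the plan.

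A version of the remedy that switched to another test when out-of-range knees turned out to be few would let the data choose the primary test. It should be avoided.

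**Conclusion.** The point holds as an inexpensive improvement. Fisher's test runs at about 2.6-2.8% near the planned rates and below 1% at about 95% in range. For site SDs up to 1.0 it gives up about 4 to 9 power points to a site-stratified CMH test. It gives up about 3 to 4 points to Boschloo's test in the calculation without site effects. Most of the gain over Fisher comes from removing discreteness. Site adds about 0 to 2 points over a pooled chi-square for SDs of 0 to 1.5, and up to about 5 under the typical-site assumption.

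A reader might infer that the trial is underpowered because of this choice. On the plan's own rates it is not: Fisher stays at or above 80% at 40 per arm, and falls to about 79% only at a site SD of 1.5. The margin is thin, though, at one patient per group.

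The power figures rest on the ±2° planning rates. The limits of ±2° and ±3° in section 7 must be reconciled before any of them is final. The site SDs and the 1:1 balance within site are assumptions, and the CMH level rests on simulation.

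**What to change.** In section 7.1, state that blocks are generated separately for each site.

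In section 7.3, prespecify one primary test with no switch that depends on the data. Suggested wording: *The primary test is the Cochran-Mantel-Haenszel test stratified by site, without continuity correction, two-sided 0.05. The Mantel-Haenszel risk difference is reported with its 95% confidence interval. Fisher's exact test is a sensitivity analysis.*

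If the sponsor wants a guaranteed exact level without stratification, name Boschloo's test as primary instead. It is never less powerful than Fisher's. In either case, rewrite the sample-size text to name the chosen test and recompute the number for it.

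The cost is a few lines of wording and no extra patients, provided that the change is made before outcome data are seen. CMH is standard in SAS. Its drawbacks should be accepted openly: it is a large-sample test, sites with no out-of-range knee contribute no information to it, and it gains nothing over a pooled test if sites do not differ.
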